## IRB#: 06-044 A(11)

#### **11.1** Toxicities/side effects

The most common toxicities associate with perifosine are nausea, vomiting, and diarrhea. NCI CTC version 3.0 will be used to grade all toxicity.

Reported Adverse Events and Potential Risks:

- Constitutional Symptoms: fatigue (lethargy, malaise, asthenia)
- Gastrointestinal: anorexia, dehydration, flatulence, diarrhea, nausea, vomiting

The following events were reported in two or fewer of the patients treated on the NCI sponsored phase I trial:

- Pulmonary: hiccoughs (hiccups, singultus)
- Renal/Genitourinary: increased creatinine
- Hepatic: increased alkaline phosphatase, increased GGT

Also reported on the NCI phase I perifosine trials and occurring in two or fewer patients with the relationship to perifosine still undetermined:

- Blood/Bone Marrow: decreased hemoglobin
- Constitutional Symptoms: fever, sweating, weight loss
- Dermatology/Skin: mild skin reaction
- Gastrointestinal: mucositis, dyspepsia/heartburn
- Neurology: lightheadedness
- Ocular/Visual: eye symptoms, specifically blurred vision, photophobia and cataract formation
- Pain: abdominal pain, headache, arthritis, arthralgia
- Genitourinary: hyperuricemia

Also from animal data:

• Dose dependent kidney and eye events (retinal degeneration and cataracts)

If hematologic toxicity grade 3 or higher occurs patients may be treated with appropriate growth factors.

#### 12.0 CRITERIA FOR THERAPEUTIC RESPONSE/OUTCOME ASSESSMENT

The primary efficacy endpoint will be progression free survival (PFS) at six months from registration. For this and for all other time to event analyses, if a patient is NOT registered on the pre-operative portion of the study (surgical arm), the start date for calculation of time to event will be the date of first study drug administration. For this and for all other time to event analysis, if a patient IS enrolled on the pre-operative portion of the study (surgical arm), the start date for calculation of time to event analysis, if a patient IS enrolled on the pre-operative portion of the study (surgical arm), the start date for calculation of time to event will be the date of the first post-operative study drug administration.

## IRB#: 06-044 A(11)

Objective status should be measured and recorded although this is not the primary endpoint. The following definitions will be used based on standard criteria for malignant glioma trials [23]:

Measurable Disease: Bidimensionally measurable lesions with clearly defined margins by CT or MRI scan.

Evaluable Disease: Unidimensionally measurable lesions, masses with margins not clearly defined.

Non-Evaluable Disease: Not Applicable for response evaluation

Objective Status, To Be Recorded at Each Evaluation: If there are too many measurable lesions to measure at each evaluation, choose the largest two to be followed before a patient is entered on study. The remaining lesions will be considered evaluable for the purpose of objective status determination. Unless progression is observed, objective status can only be determined when ALL measurable and evaluable sites and lesions are assessed.

Complete Response (CR): Complete disappearance of all measurable and evaluable disease. No new lesions. No evidence of non-evaluable disease. All measurable, evaluable and non-evaluable lesions and sites must be assessed using the same techniques as baseline. Patients must be on no steroids.

Partial Response (PR): Greater than or equal to 50% decrease under baseline in the sum of products of perpendicular diameters of all measurable lesions. No progression of evaluable disease. No new lesions. All measurable and evaluable lesions and sites must be assessed using the same techniques as baseline. The steroid dose at the time of the scan evaluation should be no greater than the maximum dose used in the first 8 weeks from initiation of therapy.

Partial Response, Non-Measurable (PRNM): Not applicable.

Stable/No Response: Does not qualify for CR, PR, or progression. All measurable and evaluable sites must be assessed using the same techniques as baseline. The steroid dose at the time of the scan evaluation should be no greater than the maximum dose used in the first 8 weeks from initiation of therapy.

Progression: 25% increase in the sum of products of all measurable lesions over smallest sum observed (over baseline if no decrease) using the same techniques as baseline, OR clear worsening of any evaluable disease, OR appearance of any new lesion/site, OR clear clinical worsening or failure to return for evaluation due to death or deteriorating condition (unless clearly unrelated to this cancer).

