## **OBJECTIVES AND SCIENTIFIC AIMS**

- Primary aim:
  - Determine the efficacy of perifosine in patients with recurrent/progressive GBMs not taking EIAEDs as measured by 6mPFS.
- Secondary aims
  - Determine molecular effects of perifosine on AKT, RAS, and proliferation in malignant gliomas by analysis of resected tissue in patients on the surgical substudy.
  - Determine metabolic effects of perifosine on malignant gliomas by PET imaging.
  - o Identify molecular features that predict perifosine response.

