## 6.1 CRITERIA FOR SUBJECT ELIGIBILITY

## 6.2 Inclusion Criteria

- Patients must have shown unequivocal evidence for tumor progression by MRI or CT scan.
- Patients must be on a stable or decreasing dose of corticosteroids for a minimum of 5 days before the baseline MRI and FDG-PET scans.

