#### 10.3 Imaging and Molecular Studies

Patients not on the surgical arm will undergo imaging evaluation with brain MRI (with MR Perfusion and MR spectroscopy if possible) at baseline and every 8 weeks Patients unable to undergo MRI will have CT scans. Patients will also undergo FDG-PET imaging of the brain (at MSKCC) at baseline and every 16 weeks (4 cycles) to assist with interpretation of MRI. Patients will also undergo a brain FDG-PET scan after 1-2 weeks of therapy at MSKCC to investigate potential metabolic effects of perifosine and to explore early FDG-PET as a predictor of response by clinical and radiographic evaluations performed later.

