## IRB#: 06-044 A(11)

Unknown: Progression has not been documented and one or more measurable or evaluable sites have not been assessed.

Best Response: This will be calculated from the sequence of objective statuses.

For patients with all disease sites assessed every evaluation period, the best response will be defined as the best objective status. If the response does not persist at the next regular scheduled MRI, the response will still be recorded based on the prior scan, but will be designated as a non-sustained response. If the response is sustained, e. g. still present on the subsequent MRI, it will be recorded as a sustained response, lasting until the time of tumor progression. Best response is unknown if the patient does not qualify for a best response or increasing disease and if all objective status determinations before progression are unknown.

Criteria permitting uni-dimensional response measurement have recently been adopted and published by an international consensus committee, Response Evaluation Criteria In Solid Tumors Group (RECIST). In order to ensure comparability of data from this trial with data from earlier trials, this trial will retain the traditional evaluation definition above as primary. However, RECIST criteria that can be collected, will be used for secondary evaluation.

Neurological Exam: Although not used for determining response, it is useful to evaluate improvement in the neurologic exam, (as compared to the baseline assessment), that should coincide with objective measurement of tumor size.

- +2 Definitely better
- +1 Possibly better
- 0 Unchanged
- -1 Possibly worse
- -2 Definitely worse

Performance Status: Patients will be graded according to Karnofsky Performance Status (see Appendix 20.1).

Time to Treatment Failure: From the treatment start date to the date of first observation of progressive disease, non-reversible neurologic progression or permanently increased steroid requirement (applies to stable disease only), death due to any cause, or early discontinuation of treatment. If a patient is NOT registered on the pre-operative portion of the study (surgical arm), the start date for calculation of time to event will be the date of first study drug administration. If a patient IS enrolled on the pre-operative portion of the study (surgical arm), the start date for calculation of time to event will be the date of the

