Up to 20 patients with anaplastic glioma and evaluable disease at study entry (i.e., did not undergo gross total resection as the most recent therapy prior to registration) will be accrued. Endpoints such as response, one-year survival probability, overall survival and progression-free survival will be computed in order to gain preliminary data for these other malignant glioma subtypes. However, the historical controls for patients with anaplastic glioma are less well defined than for GBM; therefore, only patients with GBM will be included in analyses of efficacy and the two-stage design will be applied only to the GBM cohort.

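### The steroid condition for partial response cannot fail at a scan in the first 8 weeks, so a week-8 response can be recorded after a steroid increase

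*Combined protocol and SAP*

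**What the plan says.** Section 12.0 applies one steroid condition to both PR and stable status: the dose at the scan "should be no greater than the maximum dose used in the first 8 weeks from initiation of therapy". It does not refer to the baseline dose. Complete response requires the patient to be off steroids altogether. None of the triggers listed for progression involves steroid dose.

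Under Section 10.3, patients not on the surgical arm have brain MRI "at baseline and every 8 weeks", and the surgical arm follows the same interval after surgery. Steroids are controlled at entry: Section 6.2 (Inclusion Criteria) states "Patients must be on a stable or decreasing dose of corticosteroids for a minimum of 5 days before the baseline MRI".

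Under Best Response in Section 12.0, if a response is gone at the next scheduled MRI, "the response will still be recorded based on the prior scan, but will be designated as a non-sustained response".

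Response, or something close to it, appears in three places:
- The Biostatistics section, for anaplastic glioma: "Endpoints such as response, one-year survival probability, overall survival and progression-free survival will be computed".
- The secondary aims: "Identify molecular features that predict perifosine response".
- Section 10.3, where the FDG-PET after 1-2 weeks is done partly "to explore early FDG-PET as a predictor of response by clinical and radiographic evaluations performed later".

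**The concern.** A steroid condition on response is there so that shrinkage on the scan is not credited to the drug when the patient has meanwhile been given more steroid. The protocol takes this seriously at baseline and for complete response. At the first response scan, however, the condition for PR compares the dose with a maximum that already includes that dose, so it screens nothing out.

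At stake is how response is read in small groups. The anaplastic glioma cohort is at most 20 patients, and one mislabelled PR there moves the response rate by 1/20 = 5 percentage points. The molecular and FDG-PET explorations could be blurred in the same way if they use the PR label.

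**Working it through.** **The design figures, for reference.** The two-stage rule in the Biostatistics section (12 then 37 GBM patients; stop at 0 of 12; negative at 3 or fewer of 37) reproduces by exact binomial calculation. P(positive) is 0.902 at a 6mPFS rate of 20% and 0.0935 at 5%, so P(negative) at 5% is 0.907. The stated 0.90 and 0.90 hold. Neither the rule nor the progression definition uses steroid dose, so nothing below changes these figures.

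**The condition.** Let d(t) be the steroid dose on day t and L = max of d(t) over days 1 to 56. PR or stable status at a scan on day s requires d(s) ≤ L.
- If s ≤ 56, d(s) is one of the values in the maximum, so d(s) ≤ L whatever the baseline dose. A dose doubled the week before the scan raises L along with it.
- If s > 56, d(s) > L is possible, but only through a rise made after day 56. A rise before then is already inside L.

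**Where the first scan falls.**
- *Non-surgical patients.* Eight weeks is 8 × 7 = 56 days. A scan that runs late, or that follows the two-month interval mentioned in Section 4 (31 + 28 = 59 to 31 + 31 = 62 days), leaves only a few days in which a rise could be caught.
- *Surgical arm.* Section 12.0 starts its time-to-event clocks at the first post-operative dose but does not define *initiation of therapy* for the steroid condition. If it means the post-operative restart, the argument is unchanged. If it means the first pre-operative dose, the scan falls at about day 5 + 7 + 56 = 68 or later, and a rise in the 68 − 56 = 12 or more days before it can be caught.

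**Other rules that might close the gap.**
- Evident clinical deterioration counts as progression (Section 12.0), but a patient whose symptoms are controlled on a higher dose need not be deteriorating.
- A permanent rise in steroid need counts as treatment failure (Section 12.0), but only in stable disease and only for that endpoint. It does not block a PR.
- Section 9.6.8 asks for the smallest dose that controls symptoms. This limits increases in practice but is not a response criterion.

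**Size.** The documents give neither the week-8 PR rate nor the share of patients who raise steroids early. Assume a PR rate of 5-10% and 10-30% of those PRs on a raised dose:

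| Group | Low | High |
|---|---|---|
| 37 GBM | 37 × 0.05 × 0.10 = 0.2 | 37 × 0.10 × 0.30 = 1.1 |
| 20 anaplastic glioma | 20 × 0.05 × 0.10 = 0.1 | 20 × 0.10 × 0.30 = 0.6 |

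**The case against.** The strongest reply is that the window is deliberate. Section 12.0 says its definitions follow standard malignant glioma criteria and are kept as primary so that results compare with earlier trials. Eight weeks can be read as a grace period for early steroid adjustment. This stands as a reason to leave the labels alone. It does not make the condition informative at the first scan.

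It is also fair that Section 12.0 says objective status is not the primary endpoint, and that only the anaplastic glioma paragraph names response as an endpoint, to gain preliminary data. The tissue work is described as exploring sensitivity to the drug, with no outcome variable fixed, and the Biostatistics section says these analyses are hard to prespecify. The effect on the molecular and FDG-PET analyses is therefore possible rather than established. The non-sustained label also lets a reader set unconfirmed PRs aside.

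Two stronger readings are tempting:
- *That many patients are affected.* With exponential PFS (an assumption) and a 26-week half-year, the share non-progressing at week 8 is p^(8/26). At 6mPFS of 5% to 20% this is 0.398 to 0.609, or 14.7 to 22.5 of 37. If 30% had raised steroids, that would be 4.4 to 6.8 patients. This pools stable disease with PR, and the documents attach no analysis consequence to a stable label, so it does not measure the harm.
- *That antiemetic dexamethasone sets the limit at later scans.* Sections 9.6.1 and 20.4 recommend it around the loading dose (4 mg in 20.4), and the wording does not exempt it. But Section 9.6 treats antiemetics and corticosteroids for edema separately, so the standing dose is the natural meaning. It would matter only if the antiemetic dose exceeded the patient's other steroid in weeks 1-8 and steroid was started or raised afterward. The text does not support calling this a separate defect.

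**Conclusion.** The point holds in a limited form. For an on-treatment scan on or before day 56, the steroid condition for PR and stable status is satisfied by construction. A week-8 PR can therefore be recorded after a rise from the baseline dose, and it stays on record. A later scan can be restricted, but only by a rise after day 56. A surgical-arm scan can also be restricted if therapy is counted from the first pre-operative dose.

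A reader might infer that 6mPFS is inflated through this condition. The documents do not support that: its events are progression or death due to disease, and progression has no steroid criterion. Type I error and power stand.

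The number of affected PRs is not derivable from the documents. It is probably small: about one GBM patient at most, and less than one anaplastic glioma patient, under the assumed rates. This is an inexpensive improvement to the response data for the sponsor to consider. It is not a flaw in the primary analysis.

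**What to change.** Keep the Section 12.0 objective status labels and their steroid condition unchanged, for comparability. Add the following:

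1. At each scan, record yes or no: is the standing corticosteroid dose above the dose at the baseline MRI? Short-course antiemetic dexamethasone is not counted for this flag.
2. For the surgical arm, use the dose when perifosine restarts after surgery as the reference, and define *initiation of therapy* as the first post-operative dose, in line with the time-to-event start date in Section 12.0.
3. Report response counts, and any analysis that uses response, in two ways: by the Section 12.0 definition, and with PRs seen only on flagged scans not counted as responses.

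The antiemetic exclusion should apply to the flag only. Taking those doses out of the 8-week maximum would lower the limit and could leave a non-progressing patient with no defined status. Removing flagged PRs from the main response analysis is likewise a trade-off, so both counts should be shown.

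The cost is a short paragraph and one field per scan; Section 9.6.5 already requires concomitant medications to be recorded. The downside is that, in the second count, a true responder who needed an early steroid increase is not counted until a PR is seen at or below the baseline dose.

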## IRB#: 06-044 A(11)

Unknown: Progression has not been documented and one or more measurable or evaluable sites have not been assessed.

Best Response: This will be calculated from the sequence of objective statuses.

For patients with all disease sites assessed every evaluation period, the best response will be defined as the best objective status. If the response does not persist at the next regular scheduled MRI, the response will still be recorded based on the prior scan, but will be designated as a non-sustained response. If the response is sustained, e. g. still present on the subsequent MRI, it will be recorded as a sustained response, lasting until the time of tumor progression. Best response is unknown if the patient does not qualify for a best response or increasing disease and if all objective status determinations before progression are unknown.

Criteria permitting uni-dimensional response measurement have recently been adopted and published by an international consensus committee, Response Evaluation Criteria In Solid Tumors Group (RECIST). In order to ensure comparability of data from this trial with data from earlier trials, this trial will retain the traditional evaluation definition above as primary. However, RECIST criteria that can be collected, will be used for secondary evaluation.

Neurological Exam: Although not used for determining response, it is useful to evaluate improvement in the neurologic exam, (as compared to the baseline assessment), that should coincide with objective measurement of tumor size.

- +2 Definitely better
- +1 Possibly better
- 0 Unchanged
- -1 Possibly worse
- -2 Definitely worse

Performance Status: Patients will be graded according to Karnofsky Performance Status (see Appendix 20.1).

Time to Treatment Failure: From the treatment start date to the date of first observation of progressive disease, non-reversible neurologic progression or permanently increased steroid requirement (applies to stable disease only), death due to any cause, or early discontinuation of treatment. If a patient is NOT registered on the pre-operative portion of the study (surgical arm), the start date for calculation of time to event will be the date of first study drug administration. If a patient IS enrolled on the pre-operative portion of the study (surgical arm), the start date for calculation of time to event will be the date of the

## IRB#: 06-044 A(11)

first post-operative study drug administration. As an exploratory evaluation of other means to demonstrate clinical efficicacy, the time to treatment failure in comparison to time to the most recent progression for prior relapse will also be calculated for each patient; in this manner, each patient serves as his/her own control and an increase in the time to treatment failure relative to the most recent progression may also suggest clinical activity of the drug.

Time to Death: From the treatment start date to date of death due to any cause. If a patient is NOT registered on the pre-operative portion of the study (surgical arm), the start date for calculation of time to event will be the date of first study drug administration. If a patient IS enrolled on the pre-operative portion of the study (surgical arm), the start date for calculation of time to event will be the date of the first post-operative study drug administration.

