# IRB#: 06-044 A(11)

- Comprehensive chemistry panel.
- Uric Acid
- Contrast enhanced MRI (with MR Perfusion if possible) of the brain. The same type of scan, i.e., MRI or CT, should be used throughout the period of protocol treatment for tumor measurement. Patients unable to undergo an MRI will undergo contrast enhanced CT scans. It also must be performed at least 28 days after discontinuation of prior therapy directed at VEGF/VEGFR such as bevacizumab (Avastin), VEGF-Trap, or AZD2171. Any questions regarding the definition of anti-VEGF/VEGFR therapy should be discussed with the PI or co-PI.
- **Brain FDG-PET:** It also must be performed at least 28 days after discontinuation of prior therapy directed at VEGF/VEGFR such as bevacizumab (Avastin), VEGF-Trap, or AZD2171. Any questions regarding the definition of anti-VEGF/VEGFR therapy should be discussed with the PI or co-PI.
- All brain PET scans must be performed on MSKCC scanners for adequate ability to compare scans over time.
- For patients with histologically documented malignant gliomas who will receive perifosine for their 2nd or greater relapse, the date that the most recent therapy was started will be recorded and used to calculate the time to the prior relapse for comparison with time to progression on perifosine (intrapatient comparison).

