#### 13.1 CRITERIA FOR REMOVAL FROM STUDY

All patients may continue therapy unless disease progression, death, or dose limiting toxicity is documented. The cause of death should be recorded.

The following events may be considered sufficient reason for discontinuing treatment with the study medication

- Serious toxicity due to the study drug graded according to the NCI Common Terminology Criteria for Adverse Events v3.0 [22]
- Conditions requiring therapeutic intervention not permitted by the protocol
- Unacceptable toxicity in the opinion of the patient or investigator even if not specifically defined elsewhere
- Personal preference by the patient for any reason
- Subject non-compliance with the defined treatment plan
- Medical or psychiatric illness or social environment which in the investigator's judgment renders the patient incapable of further therapy.
- Any other situation where, in the opinion of the investigator, continued participation in the study would not be in the best interest of the patient
- Treatment delay due to toxicity greater than 14 days
- Pregnancy
- Disease progression

All reasons for discontinuation of treatment must be documented in the flow sheets.

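### The protocol names two different perifosine endpoints for one exploratory within-patient comparison, and the Section 12.0 choice sets a broader composite against a progression-only interval, which biases it against the drug (minor).

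*Combined protocol and SAP*

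**What the plan says.** The within-patient comparison appears in two places.

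- **Section 8.1 (Pretreatment Evaluation).** The start date of the latest earlier treatment is collected at second or later relapse. Its stated purpose is to be "used to calculate the time to the prior relapse for comparison with time to progression on perifosine". The perifosine-side endpoint is time to progression, and the population is second or later relapse.
- **Section 12.0 (Time to Treatment Failure).** As an exploratory evaluation, the plan calculates for each patient "the time to treatment failure in comparison to time to the most recent progression for prior relapse". It treats each patient as his or her own control and reads a longer interval on perifosine as a possible sign of activity. The perifosine-side endpoint is time to treatment failure.

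Section 12.0 ends time to treatment failure at progressive disease, at non-reversible neurologic progression, at a permanently increased steroid need in stable disease, and at "death due to any cause, or early discontinuation of treatment". Section 13.1 lists reasons for discontinuation that are not progression, including toxicity, non-compliance and "Personal preference by the patient for any reason". The Biostatistics section (14.0) does not mention the comparison.

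**The concern.** One analysis has two endpoints on the perifosine side, and nothing in the documents says which governs. Two analysts following different sections would get different results from the same patients.

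The Section 12.0 choice also treats the two intervals unequally. A patient who stops perifosine for toxicity or by choice, without progression, is counted as failing on that date. The same event on the prior therapy would not have ended the prior interval, which runs on to relapse. A patient is a fair control for himself or herself only if the same events end both intervals. What is at stake is sensitivity: this comparison is meant to pick up a hint of activity, and it loses some of its ability to do so.

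**Working it through.** **Step 1. Compare what ends each interval.** The events come from the definitions of progression and time to treatment failure in Section 12.0, and from Sections 8.1 and 13.1.

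| Event | Ends prior interval | Ends perifosine interval, Section 8.1 | Ends perifosine interval, Section 12.0 |
|---|---|---|---|
| Progression | yes | yes | yes |
| Stopping for toxicity, preference or non-compliance | no | no | yes |
| Death clearly unrelated to the tumor | not applicable (patient enrolled) | no, on the progression definition | yes |

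The neurologic and steroid components of treatment failure overlap with progression, because the progression definition already includes clear clinical worsening. Death or deterioration from the tumor that prevents evaluation also counts as progression. The clear excess in Section 12.0 is therefore discontinuation for other reasons and unrelated death.

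**Step 2. Direction.** Progression is itself a treatment-failure event, so in any patient time to treatment failure cannot exceed time to progression. If time to treatment failure exceeds the prior interval, time to progression does too. The mismatch can only shorten the perifosine side.

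**Step 3. Size, as an illustration.** The plan gives no sample size, threshold or test for this comparison, so there is no stated figure to reproduce. These assumptions are not in the documents:

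- the prior and perifosine times are independent and exponential;
- the progression hazard is L in both periods (no drug effect);
- an extra hazard M of non-progression failure applies on perifosine;
- f = M/(L + M) is the share of treatment failures that are not progression.

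Since L + M = L/(1 − f):

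P(perifosine interval > prior interval) = L/(2L + M) = (1 − f)/(2 − f)

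Ratio of median time to treatment failure to median time to progression = L/(L + M) = 1 − f

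If perifosine halved the progression hazard to L/2, and f is the share under that hazard, the probability becomes 1/[1 + 0.5/(1 − f)].

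| f | P, no drug effect | Median ratio, no drug effect | P, progression hazard halved |
|---|---|---|---|
| 0 (same endpoint on both sides) | 0.500 | 1.00 | 0.667 |
| 10% | 0.9/1.9 = 0.474 | 0.90 | 0.643 |
| 20% | 0.8/1.8 = 0.444 | 0.80 | 0.615 |
| 30% | 0.7/1.7 = 0.412 | 0.70 | 0.583 |

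**Step 4. Population.** The inclusion criteria set no limit on the number of prior relapses and require failed radiation, so first-relapse patients can enroll. Section 8.1 asks for the prior-therapy start date only at second or later relapse. Read literally, the each-patient wording of Section 12.0 has no planned input for first-relapse patients.

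**The case against.** The strongest reply is that little depends on this analysis. It is labeled exploratory, is not among the aims in Section 2.0, has no threshold, and plays no part in the two-stage decision on 6-month progression-free survival in GBM. Section 8.1 is also a data-collection instruction, whereas Section 12.0 is where endpoints are defined. This stands as to weight, and it is why the point is minor. It does not settle which endpoint applies.

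Four stronger readings are tempting, and the documents do not support them.

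- **That a longer interval on perifosine becomes uninterpretable.** Step 2 of the working shows that the mismatch cannot produce a spurious increase, and an increase is the only result Section 12.0 proposes to interpret. Matching the endpoints would not establish attribution either, because the comparison remains unrandomized across lines of treatment.
- **That this is the trial's only internal control.** Section 4.1 plans intra-patient tissue comparison where prior tissue exists, and Section 10.3 plans baseline and on-treatment FDG-PET in the same patient.
- **That the two sections define conflicting populations.** Section 12.0 refers to a prior relapse, so its wording can be read as each patient who has such an interval. This is mostly loose wording that needs one clarifying clause.
- **That any steroid increase counts as failure.** Only a permanently increased requirement in stable disease does.

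The objection that the probabilities are only illustrative also stands. The share f is assumed, paired intervals in one patient may be correlated, and no rule in the plan uses 0.50 as a benchmark.

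**Conclusion.** The inconsistency holds on the text. Sections 8.1 and 12.0 name different perifosine-side endpoints for the same comparison, and the Section 12.0 version compares unlike intervals. The bias runs against perifosine, so activity can be missed but not manufactured.

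The direction follows from the definitions alone. The size rests on the exponential, independence and no-effect assumptions and on f, which the documents do not supply. Over f = 10% to 30%, the loss is about 3 to 9 percentage points from 0.50. Severity is minor, and the conclusion on the primary endpoint is unaffected.

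**What to change.** In Section 12.0:

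- Use time to progression on perifosine for the within-patient comparison, as Section 8.1 already does.
- State that the comparison applies to patients treated at second or later relapse, for whom the prior-therapy start date is recorded.
- Where a patient stops perifosine without progression, use progression observed afterward if available; otherwise censor at the last assessment. Plain censoring at discontinuation would discard later progression, and Section 14.0 plans six months of follow-up for all patients.
- State a rule for unrelated death, and name an analysis that allows for paired data with censoring on the perifosine side.
- Report time to treatment failure separately.

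Defining the prior interval as time to treatment failure would also match the two sides, but it would require dates and reasons for stopping the prior therapy, which Section 8.1 does not ask for.

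The cost is a short text change and slightly more analysis work. The downside is that censoring may be informative when patients who stop early differ in prognosis, and the report should say so.
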